## 10.2. Exposure and Compliance

The duration of study drug exposure is defined as the number of days on treatment from the first dose of study drug until the last dose of study drug (last dose – first dose + 1). Study drug exposure is summarized by descriptive statistics. Summaries include the total dose (mg) received (based on the number of pills returned), study drug compliance, and duration (days) of exposure during the study treatment period. In addition, a summary of the number and percentage of patients by dose (placebo, 5 mg, 10 mg, 20 mg, 30 mg) and by visit is generated. If a patient received more than one dose during a visit window, the duration of the longest dose exposure is used to calculate study drug dose during a given visit window. Summaries of the number and percentage of patients by dose include a subgroup analysis by baseline ACR ( $ACR \leq 300$  mg/g vs.  $ACR > 300$  mg/g).

Total number of doses dispensed and total dose (mg) dispensed is calculated from total number of kits (bottles) recorded on the Study Drug Dispensation eCRF. Total number of doses received is calculated from information on the eCRF of Study Drug Return and Study Drug Dispensation, as the (total number of doses dispensed – total number of doses returned). Study drug compliance (%) is calculated as  $100 \times \text{total number of doses received} / \text{total number of study days of study participation}$ , excluding the off-treatment periods between Week 48 to Week 52 and Week 100 to Week 104.

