**Duration of study:**

100 weeks of treatment plus a 4-week follow-up

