#### 6.5.4.1. Off-Treatment Visit Windows

Patients who permanently discontinue study drug prior to Week 100 are asked to resume the planned assessments according to the study schedule in the protocol. Off-treatment values for clinical laboratory evaluations (Section 10.5), vital signs (Section 10.6), and electrocardiograms (Section 10.8) are those that occur after the last dose date for patients permanently discontinuing study drug prior to Week 100, and is summarized relative to their last dose of study drug. Off-treatment safety assessments are grouped for analyses according to the strategy in Table 4. Assessments that occur on the date of last dose are considered on treatment.

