### **8.6.1. Primary Analysis of the Year 1 Primary Efficacy Endpoint**

The Year 1 primary endpoint of this study is the change in eGFR at Week 48 (i.e., the end of the first year of drug exposure). The change from baseline eGFR for patients treated with bardoxolone methyl is compared with placebo at Week 48 using mixed models repeated measures (MMRM) analysis, with baseline eGFR (BASE\_eGFR), ACR strata (ACR\_STRAT), and fraction of one-year exposure to treatment (TRT\_EXP1) as covariates and the following fixed factors: treatment group (TRT), time (i.e., VISIT; analysis visit number), the interaction between treatment and time (TRT x VISIT), and the interaction between baseline eGFR and time (BASE\_eGFR x VISIT) as covariates. Inclusion of the fraction of expected one-year exposure to treatment (Section 6.5.11) in the MMRM model as a covariate provides an adjustment for eGFR values collected from early discontinuation patients having less than 1-year of drug exposure.

The trial design separates discontinuation of study drug from discontinuation of study follow-up. Therefore, patients may discontinue early from study drug while continuing follow-up with study visits and assessments. The primary analysis of eGFR at Week 48 uses available eGFR values irrespective of whether or not a patient is receiving treatment. The MMRM analysis uses all eGFR values collected through Week 48 according to analysis visits 0, 1, 2, 4, 6, 8, 12, 24, 36, and 48 (Section 6.5.4). An unstructured covariance matrix is used.

In the event the MMRM model with an unstructured covariance structure does not converge, the following covariance structures are substituted, in the order listed. Each subsequent covariance structure is used only if each previous covariance structure is used and no previous model converged.

1. Heterogeneous Toeplitz covariance structure (assuming different variances at each time point and that measurements taken closer together in time are more highly correlated than those taken farther apart).
2. Toeplitz covariance structure (assuming measurements taken closer together in time are more highly correlated than those taken farther apart).
3. First order auto-regressive [AR(1)] covariance structure (assuming measurements taken closer together in time are more highly correlated than those taken farther apart, but the correlation is more constrained than the Toeplitz structure).

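### The compliance formula in SAP 10.2 counts off-drug follow-up days as missed doses, so fully adherent patients who stop study drug but stay in the trial score low

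*SAP*

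**What the plan says.** SAP Section 10.2 takes doses received as "total number of doses dispensed – total number of doses returned". Compliance is 100 times that number over the "total number of study days of study participation", "excluding the off-treatment periods between Week 48 to Week 52 and Week 100 to Week 104". No other days are removed.

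The same section defines duration of exposure as the "number of days on treatment from the first dose of study drug until the last dose of study drug", that is, last dose minus first dose plus 1. The compliance formula does not use this quantity.

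Stopping drug and leaving the trial are separate events in this design. SAP Section 8.6.1 says that "patients may discontinue early from study drug while continuing follow-up with study visits and assessments". SAP Section 6.5.4.1 adds: "Patients who permanently discontinue study drug prior to Week 100 are asked to resume the planned assessments". The disposition summary in SAP Section 7.1 has a line in each year for patients who stopped treatment early but went on with study visits.

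The SAP addendum corrects the exposure covariate (its Section 3.1) and discusses temporary treatment interruptions (its Section 4.4.3). It does not change Section 10.2.

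**The concern.** A compliance percentage should say how much of the drug that was due was taken. The formula takes out the two planned breaks, when no dose is due. It does not take out the days after permanent discontinuation, when no dose is due either. Each such day enters the denominator with nothing to match it in the numerator.

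The score of an early stopper therefore depends on when drug was stopped and on how long the patient stayed in follow-up, and not only on adherence. Two patients with the same dosing record can score very differently because one agreed to keep attending visits. SAP Section 10 presents safety summaries by treatment group, so a difference between arms in the number or timing of discontinuations, or in retention after stopping, could be read as a difference in adherence.

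**Working it through.** The documents state no compliance figure, so there is none to reproduce. The check applies the formula to patients whose true adherence is known.

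**Inputs**
- Study length: "100 weeks of treatment plus a 4-week follow-up" (SAP synopsis), so 104 weeks = 728 days.
- Days removed: Weeks 48 to 52 and Weeks 100 to 104, 28 days each (SAP 10.2).
- Dosing: one dose per day (SAP synopsis). Patients under 18 start on alternate days for one week. That costs about three doses, (672 − 3)/672 = 99.6% over the full course, and is ignored here.
- Assumption: each test patient takes every dose until the stop and returns everything unused.

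**Denominator with follow-up to Week 104**

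728 − 28 − 28 = 672 days.

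**Fully adherent patients, followed to Week 104**

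| Permanent stop | Doses received | SAP 10.2 compliance | First-to-last-dose denominator |
|---|---|---|---|
| After 100 doses | 100 | 100/672 = 14.9% | 100/100 = 100% |
| Week 24 | 168 | 168/672 = 25.0% | 168/168 = 100% |
| Week 48 | 336 | 336/672 = 50.0% | 336/336 = 100% |
| Week 76 | 532 − 28 = 504 | 504/672 = 75.0% | 504/(532 − 28) = 100% |
| Week 88 | 616 − 28 = 588 | 588/672 = 87.5% | 588/(616 − 28) = 100% |
| Week 100 | 700 − 28 = 672 | 672/672 = 100% | 672/(700 − 28) = 100% |

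**Same dosing, different follow-up**

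Footnote k to the schedule of assessments (SAP Table 2) asks patients who terminate before Week 100 to attend an end-of-treatment visit and a follow-up visit four weeks later. Counting those 28 days as participation:
- stop after 100 doses: 100/(100 + 28) = 78.1%, against 14.9% with follow-up to Week 104;
- stop at Week 24: 168/(168 + 28) = 85.7%, against 25.0%.

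**Year 1 data alone**

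The denominator is 364 − 28 = 336 days. Stops at Weeks 12, 24 and 36 give 84/336 = 25%, 168/336 = 50% and 252/336 = 75%.

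**Effect on an arm mean**

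The documents give no discontinuation rates. Suppose a fraction q of an arm stops, stop times are uniform over the dosing days, all stoppers are followed to Week 104, and everyone adheres fully while on drug. Stoppers then average 50%, and the arm mean is 100 × [(1 − q) + 0.5q]:
- q = 5%: 97.5%
- q = 10%: 95.0%
- q = 20%: 90.0%
- q = 30%: 85.0%

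**Does the alternative denominator still detect missed doses?**

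Yes. A patient who misses 20 of 168 doses before stopping at Week 24 scores 148/168 = 88.1%.

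**The case against.** The best defence is that Section 10.2 intends an on-treatment measure. It introduces the summaries as covering "duration (days) of exposure during the study treatment period", and it removes planned off-drug time. On that reading the wording is merely loose. The intent is plausible, but the phrase sits in the list of summaries, while the formula names its own denominator and does not refer back. A programmer who follows the formula gets the figures above.

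A second defence is that doses received over planned treatment days is a legitimate measure of how much of the intended course was delivered. It is, but the SAP does not label it so, and participation days are not planned days: a patient who leaves early has a smaller denominator than one who stays.

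A third defence is that the reader can see the cause elsewhere. SAP Section 7.1 already reports discontinuation, and exposure duration is summarised beside compliance. This stands as mitigation, and no new discontinuation table is needed. It does not make the compliance figure itself correct.

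Some stronger readings that a reader might infer are not supported:
- *The denominator is every day in the study.* It is not; 56 planned days are removed.
- *A patient who leaves on stopping scores about 100%.* With the four-week follow-up visit the 100-dose patient scores about 78%.
- *All early stoppers look grossly non-compliant.* Late stops score 75% (Week 76) to 87.5% (Week 88).
- *The arm with more discontinuations must look less adherent.* Timing and retention matter too. As an illustration, 10% stopping at Week 24 lowers an arm mean by 0.10 × 75 = 7.5 points, while 20% stopping at Week 88 lowers it by 0.20 × 12.5 = 2.5 points.

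**Conclusion.** The point holds. As written, the formula gives the wrong compliance figure for any patient who stops drug early and remains in follow-up. For a fully adherent patient followed to Week 104 it gives 14.9% after 100 doses and 87.5% for a stop at Week 88, where the correct figure is 100%. These results rest on once-daily dosing, complete returns and follow-up to Week 104. The arm-level figures also rest on assumed discontinuation rates and uniform stop times. A spurious difference between arms is possible, not certain.

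The consequence is small. A reader might infer that efficacy results are affected, but the documents do not support that. The exposure covariates are built from dose dates (SAP Section 6.5.11; addendum Table 2). The stated per-protocol criteria (SAP Sections 6.3.2 and 6.3.3) set no compliance threshold. SAP Section 10 rules out formal testing of safety data. What needs correcting is one descriptive summary.

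**What to change.** In SAP Section 10.2, replace the denominator with the days from first to last dose (last dose − first dose + 1, already defined there), less the planned Week 48 to 52 off-drug period where it falls within that span. For tables by treatment year, apply the same rule to the first and last dose within the year.

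State how temporary interruptions are handled. Gaps that patients made on their own initiative should stay in the denominator, because they are non-adherence and subtracting them would inflate the figure. If any interruptions are excluded, limit this to those directed by the protocol or the investigator.

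Leave discontinuation to the disposition summary in SAP Section 7.1.

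The cost is one sentence of SAP text and one derivation from dose dates that the plan already uses. No new data are needed, unless interruptions are to be excluded and their cause is not already recorded.

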## 10.3. Concomitant Medications

Concomitant medications are coded using the World Health Organization (WHO) drug dictionary (Enhanced version, March 2016, B2 format) for anatomical therapeutic chemical classification (ATC) and preferred drug name. A patient who used multiple medications is counted only once for each ATC and preferred drug name. ATC and preferred drug name within each ATC are sorted alphabetically. Coded concomitant medications are summarized by treatment by WHO ATC class and preferred name. Percentages are based on the number of patients in the safety analysis set. Each summary is ordered by descending order of incidence of ATC class and preferred name within each ATC class.

A concomitant medication is any medication taken at the time of first study treatment or a medication that was started after the start of study drug dosing. Specifically, concomitant medications are medications

- that are continued from screening and continued after the first study drug dosing, or
- that have start dates or stop dates within the treatment period, or
- that have no end date.

Medications with an end date on the date of first study drug administration are not considered concomitant medications.

Patients who take excluded medications (defined in the Protocol Section 9.3.1) during the study are listed.

### **10.3.1. Missing and Partial Concomitant and Other Medication Start and Stop Dates**

Missing and partial concomitant medication start and stop dates are detailed in Section 6.6.2.

### **10.4. Prior and Concomitant Procedures and Surgeries**

Prior and concomitant procedures and surgeries are listed.

### **10.5. Clinical Laboratory Evaluations**

Laboratory data are summarized at baseline and at each time point by treatment.

#### **10.5.1. Continuous Summaries of Laboratory Results**

Selected laboratory evaluations and change from baseline are summarized by treatment, laboratory category (hematology, chemistry), test, and study visit using continuous statistics. The estimated glomerular filtration rate (eGFR) results are calculated using formulas described in Section 6.5.6.

The change from baseline in select laboratory evaluations at protocol endpoint time points (i.e., Week 48, 52, 100, and 104) for patients treated with bardoxolone methyl compared to placebo may be performed using the analysis of covariance (ANCOVA) model described in Section 8.7.1 and Section 8.9.1 .

Box plots and line graphs are generated for selected laboratory test results, such as eGFR, ACR, alanine aminotransferase (ALT), aspartate aminotransferase (AST), total bilirubin, BNP, BUN, uric acid, magnesium, creatinine, and creatine kinase (CK). Line graphs include mean  $\pm$  SE over time for both the observed values and for change from baseline.

Due to the nature of urinalysis parameters, summaries of continuous statistics are not provided unless otherwise specified. The one exception is the urine albumin to creatinine ratio (ACR) from the first morning void urine collection. Qualitative lab results, including urinalysis, are included in the listings, but are not summarized. Laboratory results that are above or below normal limits are flagged in the listings.

Summaries of ACR (Section 6.5.7) will use the geometric mean with 95% confidence intervals instead of the arithmetic mean and will display ACR results in original units of mg/g. Changes from baseline in ACR are reported as the post-baseline/baseline ratios and are summarized by geometric means with 95% confidence intervals at each time point. Summaries of ACR will use the geometric mean instead of the arithmetic mean. Presentations will display ACR results in the original units (mg/g). Changes in ACR are calculated as the ratio of each visit to baseline. Similar ANCOVA analyses as described in this section will be performed for ACR ratio to baseline.

Additionally, ACR is summarized by baseline ACR quartile. Descriptive summaries at each visit include the standard deviation, geometric mean of ACR, as well as the geometric mean of % change from baseline. Summaries of ACR exclude values within the Week 2 and Week 6 visit windows.

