### **8.7. Year 1: Key Secondary Endpoint**

#### **8.7.1. Primary Analysis of Year 1 Key Secondary Endpoint**

The Year 1 key secondary endpoint of this study is the change in eGFR at Week 52 (i.e., 4 weeks following the last dose after one year of drug exposure). Analysis of Week 52 assesses the preserved drug benefit (relative to placebo) following withdrawal of treatment; therefore, analysis of Week 52 data does not include the eGFR values collected during treatment.

The change from baseline eGFR at Week 52 for patients treated with bardoxolone methyl is compared to placebo using an analysis of covariance (ANCOVA) model, with BASE\_eGFR,

ACR\_STRAT, and TRT\_EXP1 as covariates, and TRT as the fixed effect. Inclusion of the fraction of expected one-year exposure to treatment (TRT\_EXP1; Section 6.5.11) in the ANCOVA model as a covariate provides an adjustment for eGFR values collected from early discontinuation patients having follow-up collected after less than 1-year of drug exposure.

The ANCOVA analysis uses eGFR values collected in the Week 52 analysis window (Section 6.5.4), which includes the follow-up assessment for patients who discontinued treatment early in the first year. Missing Week 52 eGFR data are imputed as defined in Section 8.5.3 using standard imputation.

The difference between bardoxolone methyl and placebo in change from baseline of eGFR is estimated along with the 95% confidence interval at Week 52.

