## **8.9. Year 2: Key Secondary Endpoint**

### **8.9.1. Primary Analysis of the Year 2 Key Secondary Endpoint**

The Year 2 key secondary endpoint of this study is the change in eGFR at Week 104 (i.e., 4-weeks following the last dose after two years of drug exposure). Analysis of Week 104 assesses for retained drug benefit (relative to placebo) following withdrawal of treatment; therefore, the analysis of Week 104 data does not include eGFR values collected during treatment.

The change from baseline eGFR at Week 104 for patients treated with bardoxolone methyl are compared with placebo in a manner similar to the ANCOVA analysis of Week 52 in Year 1 (Section 8.7.1) with the following modification:

- TRT\_EXP2 is added as a covariate and TRT\_EXP1 is removed

The analysis uses eGFR values collected in the Week 104 analysis window (Section 6.5.4), which includes the follow-up assessment for patients who discontinued treatment early in the second year. Discontinuing treatment in the second year requires that patients received at least one dose of study drug in the second year. Missing Week 104 eGFR data are imputed as described in Section 8.5.3.

The difference between bardoxolone methyl and placebo in change from baseline of eGFR are estimated along with the 95% confidence interval at Week 104.

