## 10. SAFETY AND TOLERABILITY

Safety and tolerability are evaluated by AEs, SAEs, clinical laboratory test results, body weight, vital signs, 12-lead ECG findings, physical examination, visual acuity, and audiology assessment. All analyses of the safety data are performed using the safety analysis set.

Descriptive statistics are presented by treatment group assignment in the safety analysis set. No formal statistical testing is performed for safety analyses. Safety is also summarized by the subgroups defined in Section 8.3. On-treatment values are summarized according to the analysis study windows in Section 6.5.4; off-treatment values are summarized according to the analysis study windows in Section 6.5.4.1. Safety data summaries are grouped by treatment year.

Continuous safety parameters (including selected clinical chemistries and vital signs) may be summarized using the methodology described in Section 8.6.1, Section 8.7.1, Section 8.8.1, and Section 8.9.1. Only the visit windows outlined in Table 3 are included in these analyses.

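### The borrowed eGFR models specify no own-baseline covariate for laboratory values, vital signs or, beyond three screening classes, ACR (minor)

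*SAP*

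**What the plan says.** Three statements in the safety chapter of the SAP send non-eGFR outcomes to the eGFR models.

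- Laboratory values (Section 10.5.1, optional): comparisons of change at Weeks 48, 52, 100 and 104 "may be performed using the analysis of covariance (ANCOVA) model described in Section 8.7.1 and Section 8.9.1".
- ACR (Section 10.5.1, mandatory): "Similar ANCOVA analyses as described in this section will be performed for ACR ratio to baseline".
- Other continuous safety parameters (Section 10, optional): "Continuous safety parameters (including selected clinical chemistries and vital signs) may be summarized using the methodology described in Section 8.6.1", with Sections 8.7.1, 8.8.1 and 8.9.1 listed as well.

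The models themselves are written for eGFR. In Section 8.7.1 the Week 52 change is "compared to placebo using an analysis of covariance (ANCOVA) model, with BASE\_eGFR", continuing with "ACR\_STRAT, and TRT\_EXP1 as covariates, and TRT as the fixed effect". Section 8.9.1 makes one modification: "TRT\_EXP2 is added as a covariate and TRT\_EXP1 is removed". The MMRM of Section 8.6.1 is fitted "with baseline eGFR (BASE\_eGFR), ACR strata (ACR\_STRAT), and fraction of one-year exposure to treatment (TRT\_EXP1) as covariates", plus treatment, visit and the interactions of treatment and of baseline eGFR with visit. Table 8 defines BASE_eGFR as baseline eGFR. SAP addendum Section 4.4.2 adds region to the Week 100 and Week 104 models and does not touch this point.

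Own baselines are already derived. Section 6.4.3 averages all pre-dose measurements for laboratory values and vital signs, and Section 6.4.4 takes the last pre-dose value for ACR.

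**The concern.** When change from baseline is the response, the usual companion covariate is the baseline of the same variable. It removes the part of the change that baseline predicts, and it corrects the arm difference for chance baseline imbalance. Baseline eGFR does this for eGFR. For blood pressure, magnesium or transaminases it generally does not.

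A literal reading is plausible. Where this SAP alters a borrowed model it says so, as Sections 8.8.1 and 8.9.1 do for the exposure term, but Sections 10 and 10.5.1 list no alteration. Section 9.2 writes out the ANCOVA for the PGIC and keeps BASE_eGFR. That is no error there, since the PGIC has no baseline of its own, but it shows the term being carried over. Two programmers could fit different models and both claim to follow the plan.

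ACR matters most because its analysis is mandatory and Section 10.5.2 counts it among the parameters of specific interest. Since safety is reported descriptively, readers will rely on the estimates and intervals, where lost precision and chance imbalance would show.

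**Working it through.** **The plan's own figure.** No power or precision is stated for ACR, laboratory values or vital signs. The only figure attached to the borrowed ANCOVA is for eGFR (Section 4.3.2): 80% power at 4.0 and 50% at about 2.9, with SD 8, 78 and 79 patients, and two-sided 0.025. The standard error is 8 × √(1/78 + 1/79) = 1.28. The t-test gives 80.7% power at 4.0, 50.4% at 2.9, and a critical difference of 2.89. The figure reproduces. The point concerns specification only.

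**Terms in the borrowed models**

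| Outcome | Wording | Continuous baseline covariate | Own baseline present? |
|---|---|---|---|
| Laboratory values | the model of 8.7.1 and 8.9.1 | BASE_eGFR | not specified (eGFR itself excepted) |
| Vital signs and other continuous parameters | methodology of 8.6.1 to 8.9.1 | BASE_eGFR | not specified |
| ACR ratio | similar ANCOVA | BASE_eGFR | only as ACR_STRAT, three classes |

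**Laboratory values and vital signs.** Assume unit variance for a single measurement, a common correlation r between any two measurements on a patient, a baseline that averages k pre-dose values, and other covariates unrelated to the parameter. The documents give no r for these parameters, so it is an assumption. As extracted, the schedule (SAP Table 2) shows k = 3 for chemistry (Screen A, Screen B, Day 1) and k = 2 for vital signs (Screen A, Day 1).

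- Variance of change: (1 − r)(1 + 1/k).
- Residual variance with own baseline: 1 − r²/(r + (1 − r)/k).

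For k = 3 and r = 0.5 these are 0.5 × 4/3 = 0.667 and 1 − 0.25/0.667 = 0.625. The ratio is 0.9375, a 6% reduction.

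| r | k = 3 | k = 2 |
|---|---|---|
| 0.5 | 0.667 to 0.625: 6% | 0.750 to 0.667: 11% |
| 0.7 | 0.400 to 0.388: 3% | 0.450 to 0.424: 6% |
| 0.8 | 0.267 to 0.262: 2% | 0.300 to 0.289: 4% |

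Intervals would be about 1% (√0.981 = 0.990) to 6% (√0.889 = 0.943) narrower.

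**Chance imbalance.** With 78 and 79 patients, the standard error of the baseline difference is √(1/78 + 1/79) = 0.16 SD for a single value. For an average it is multiplied by √(r + (1 − r)/k). The slope of follow-up on baseline is r/(r + (1 − r)/k). Take r = 0.5 and an imbalance of 1.9 standard errors:

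- k = 3: imbalance 1.9 × 0.16 × 0.816 = 0.25 SD, slope 0.75, shift in the change difference 0.25 × 0.25 = 0.06 SD.
- k = 2: imbalance 1.9 × 0.16 × 0.866 = 0.26 SD, slope 0.667, shift 0.333 × 0.26 = 0.09 SD.

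In both cases the shift runs against the direction of the baseline imbalance.

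**ACR.** ACR_STRAT has classes up to 300, over 300 to 1000, and over 1000 to 3500 mg/g (Section 6.5.7.2). Section 4.4 caps macroalbuminuria at about 40%, so about 60% or more of patients share the lowest class. Log ACR was simulated with an assumed median of 100 to 200 mg/g and a log-SD of 1.6. The residual variance with ACR_STRAT alone was compared with that of ACR_STRAT plus log baseline ACR.

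- Stratum formed from the baseline sample itself, r = 0.5 to 0.9: excess variance 1.02 to 1.14 times. The stratum recovers 54 to 67% of the available gain.
- Stratum from a separate screening sample, r = 0.7 to 0.9: excess variance 1.10 to 1.30 times. The stratum recovers almost none of the gain.

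Intervals would be about 1% (√1.02) to 14% (√1.30) wider.

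**The case against.** The strongest reply is that the plan does not say the eGFR model is reused unchanged. A reader might infer that from the laboratory sentence, which does cite the model as it stands. But the ACR sentence asks for *similar* analyses and Section 10 refers to *methodology*. Either word leaves room to change an outcome-specific baseline term. For ACR and vital signs the gap is an unspecified covariate, not a decision to omit one. Section 8 also places further detail in a programming conventions document that is not among the documents reviewed. It is cited for the efficacy analyses and not in Section 10, so it cannot be assumed to close the gap, but it might.

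A reader might also infer that the ACR comparison is unadjusted for ACR. It is not, because ACR_STRAT is in the model and randomisation is stratified by it. Section 4.4 applies the macroalbuminuria cap to Screen B ACR, and the schedule as extracted shows pre-dose urine collection for ACR only at Screen B. If that is right, the stratum is a coarse form of baseline ACR and the lower range of excess variance applies. The extracted table may be broken, so both ranges are shown.

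Two further inferences go too far. One is that variance would fall by 25%, 15% and 10% at r = 0.5, 0.7 and 0.8. That is the single-measurement formula, 1 − (1 + r)/2, and Section 6.4.3 defines these baselines as averages. The other is that the omission biases the comparison. Under randomisation, regression to the mean is equal in expectation in both arms, so only chance imbalance is left.

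Baseline eGFR is also not irrelevant everywhere. It is calculated from serum creatinine, and the SAP deliberately looks at ACR adjusted for filtration rate (Section 6.5.10).

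All of these limits stand. What remains is that no section names the analysed parameter's own baseline as a covariate.

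**Conclusion.** The point holds and is minor. As written, the model-based comparisons of laboratory values, vital signs and ACR have baseline eGFR as their only continuous baseline covariate. For ACR, own baseline enters only through three screening classes, the lowest covering everything up to 300 mg/g.

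The size is modest: about 2 to 11% of residual variance for laboratory values and vital signs with two or three averaged pre-dose values (r of 0.5 to 0.8), and about 1.02 to 1.30 times excess variance for ACR. These figures rest on assumed correlations, equal variances and an assumed ACR distribution, because the documents supply none of them.

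The laboratory and vital-sign models are optional, and Section 10 rules out formal safety testing. None of these comparisons is in the testing sequence of Section 8.4. A reader might infer that the eGFR results or type I error control are compromised. They are not: for eGFR, BASE_eGFR is the own baseline, and the primary and key secondary analyses are untouched.

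**What to change.** Add to SAP Sections 10 and 10.5.1:

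> For parameters other than eGFR, the baseline value of the analysed parameter as defined in Section 6.4 (and its interaction with visit in the MMRM) is included as a covariate, and ACR_STRAT is retained. For ACR, the response is the log ratio to baseline and the covariate is log baseline ACR.

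This leaves baseline eGFR free to stay in the model. It also makes the ACR response explicit, in line with the log transformation already stated in Section 6.5.7. The cost is two sentences and one extra model term. No new data or derivation is needed, since Sections 6.4.3 and 6.4.4 already define the baselines. If the text is settled before the database lock, the covariate is not chosen with results in view. If it is changed later, Section 2.2 already requires a substantive change to be identified in the CSR.
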